Study Design: In order to test the effectiveness of the x-IHPC intervention, outcomes from participants in this pilot study will be compared with outcomes from a comparison group of similar participants who receive standard nutrition counseling during their regularly scheduled check-ups. The team will enroll 25 children in the x-IHPC intervention and the same number in the comparison group (n=50). Both groups will receive standard in-office counseling, but the intervention group will also receive the x-IHPC.

Study Methodology: The comparison group receives standard, in-office counseling at visits 1, 3-months and 6-months. The intervention group receives standard in-office counseling at the same intervals, and also participates in a 12-week x-IHPC developed by a dietitian curriculum specialist. In addition, a key pillar of this study is identifying and training Community Health Workers (CHWs) to be Spanish-speaking facilitators of the x-IHPC and utilizing community engagement strategies. Training these CHWs and including them in designing the x-IHPC curriculum, will ensure that the programming is culturally appropriate; includes local features that relate directly to the community's needs; and enables study facilitators to respond effectively to the questions and learning needs of the parents and children involved in the program.

Statistical Methodology:

To examine the research question, a longitudinal analysis using generalized estimating equations (GEE) will be conducted to assess if mean differences exist on dietary measures, screen time, physical activity and guardian self-efficacy and confidence between the intervention and comparison groups while accounting for the correlation among the repeated measurements and controlling for covariates.

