2.4. Number of Subjects

The team will enroll 25 children in the x-IHPC intervention and the same number in the comparison group (n=50).

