3.4. Endpoints/Outcomes Measurements

3.4.1. Primary outcomes.

3.4.2.

Primary outcomes measured via a survey, which will include food frequency questionnaires, screen time estimates, physical activity questionnaires, estimated screen time reports, and guardian self-efficacy and confidence questions related to modifiable lifestyle behaviors.^{15 16 17} Survey data will be collected during phone calls from the PI or CHW at the outset of the study and then again at the conclusion of the study. An example survey has been included (Appendix C: Survey). The survey questions may be altered or deleted based on feedback from the study advisory board or the CHWs, as this study is based on community engagement and feedback. The final survey instrument will be submitted to this IRB for approval before the data collection begins.

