3.4.3. Secondary outcomes

BMI percentile of children and guardians enrolled in the study. This will be measured at each office visit by a trained medical assistant or the physician.

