4.2. Method of Data Analysis

Analyses will follow the intention-to-treat principle, which categorizes participants by their treatment assignments regardless of adherence to the intervention or incomplete follow-up, and includes them in all analyses. Descriptive statistics will be calculated and reported as mean, standard deviation and 95% confidence intervals for continuous variables and frequency and percentage for categorical variables. Characteristics of study participants will be compared at baseline between the intervention and control groups and tested for significance using the two-sample t-test for continuous variables and the Chi-square test for categorical variables. Comparisons that are significant at the $P<0.10$ level will be considered for inclusion in multivariable models for primary and secondary analyses given that participants will not be randomized to their respective treatment groups.

Primary analyses will examine diet quality, screen time, physical activity, and guardian self-efficacy and confidence of those in the intervention and control groups while controlling for the correlated nature of the repeated measures within participants (i.e. baseline, post-intervention, and 6-month post-intervention). Secondary analyses will compare the BMI of guardians and BMI percentile of children at the three time points between the intervention and control groups. A longitudinal data analysis strategy will be employed with generalized estimating equations with robust CIs for both primary and secondary outcomes (Albert, 1999; Ma et al., 2012). A 2-sided p-value <0.05 will be accepted to indicate statistical significance. Additional analyses will be conducted to determine if results were influenced by other covariates including demographics (age, gender, educational attainment of guardian, income, etc.). All analyses will be conducted in SAS version 9.2.

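### Robust GEE intervals at 25 per arm have no stated small-sample correction; if uncorrected, they are about 4.5% too narrow for continuous outcomes (minor, cheap to fix)

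*Combined protocol and SAP*

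**What the plan says.** Section 4.2 (Method of Data Analysis) commits the trial to "generalized estimating equations with robust CIs for both primary and secondary outcomes". It adds that "A 2-sided p-value <0.05 will be accepted to indicate statistical significance". Sections 2.4 and 4.1 set enrolment at 25 per arm, so the GEE has 50 independent participants. Neither 4.2 nor any other section names a bias correction, degrees of freedom or a reference distribution. Section 4.2 cites two methods papers, whose content cannot be checked here.

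Three other statements decide which calculation applies:

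- **Time points.** For BMI, 4.2 says: "Secondary analyses will compare the BMI of guardians and BMI percentile of children at the three time points between the intervention and control groups". Section 3.4.3 says of BMI that "This will be measured at each office visit by a trained medical assistant or the physician", and the Abstract says that the comparison group "receives standard, in-office counseling at visits 1, 3-months and 6-months", with the same intervals for the intervention group. For the primary outcomes the text is not consistent. Section 4.2 lists three repeated measures, but section 3.4 has the survey collected "at the outset of the study and then again at the conclusion of the study", which is twice.
- **Covariates.** Baseline variables that differ at P<0.10 "will be considered for inclusion in multivariable models for primary and secondary analyses". Their number is not fixed.
- **Leavers.** Section 3.6 excludes the data of anyone who leaves or is withdrawn, whereas 4.2 states intention-to-treat with everyone included. Under 3.6 the analysed number can fall below 25 per arm.

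**The concern.** The ordinary sandwich variance is built from raw residuals, which are on average too small because the model was fitted to the same data. With few participants it therefore underestimates the true variance. A normal critical value adds to this by ignoring the uncertainty in the variance estimate. For continuous outcomes both errors make intervals too narrow and p-values too small.

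At stake is whether the stated 95% and 5% are met for BMI and for any survey score analysed as continuous. The shortfall would recur in every such comparison and would favour declaring a difference. Silence also leaves the choice of variance and reference distribution open until the data are in hand.

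**Working it through.** The plan gives no power, effect size, SD or coverage figure, so there is nothing of its own to reproduce.

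**Inputs.** From the documents: n = 25 per arm (2.4, 4.1), two-sided 5% and robust intervals (4.2). Assumed: uncorrected Wald form with normal or chi-square reference, normal outcome, equal arms, complete data and no covariates. No dropout rate is given, so 20 and 15 analysed per arm are assumptions, prompted by section 3.6.

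**Step 1: single contrast (1 df), such as the between-arm difference in change.** The uncorrected sandwich SE equals the usual SE times √((n−1)/n). At n = 25 the factor is √(24/25) = 0.9798.

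- Effective critical value: 1.960 × 0.9798 = 1.920, against t(48 df) = 2.011.
- Width ratio: 1.920/2.011 = 0.955, which is 4.5% too narrow.
- Half-width in SD of change: 1.920 × √(2/25) = 0.543, against 2.011 × √(2/25) = 0.569.
- Type I error: P(|t48| > 1.920) = 0.0608, so coverage is 93.9%.

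A GEE simulation (three visits, assumed within-person correlation 0.5, no covariates, 6,000 replicates) gave 94.2%, which agrees within Monte Carlo error.

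**Step 2: joint group-by-time Wald test over three time points (2 df).** The uncorrected Wald statistic is Hotelling's T² times n/(n−1). The level at n = 25 is P(F(2,47) > (47/96) × 5.991 × 24/25) = P(F(2,47) > 2.816) = 0.0700.

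**Step 3: fewer analysed.** The same formulas give:

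| Per arm | 1-df level | 1-df coverage | Too narrow by | 2-df level |
|---|---|---|---|---|
| 25 | 6.1% | 93.9% | 4.5% | 7.0% |
| 20 (assumed) | 6.4% | 93.6% | 5.6% | 7.6% |
| 15 (assumed) | 6.9% | 93.1% | 7.6% | 8.6% |

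**Step 4: covariates.** Null simulation with 100,000 replicates (Monte Carlo SE at most 0.0009): person-level change regressed on group plus 0, 3 or 5 standard-normal covariates, 25 per arm.

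| Method | 0 | 3 | 5 |
|---|---|---|---|
| Uncorrected Wald | 6.2% | 7.1% | 7.7% |
| Kauermann-Carroll with t | 5.0% | 5.1% | 5.1% |
| Mancl-DeRouen with t | 4.6% | 3.9% | 3.6% |

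This inflation arises only when the covariates enter the tested contrast. In a linear model with complete data, baseline covariates added as main effects leave the group-by-time contrast unchanged.

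**Step 5: power at 25 per arm for an assumed difference of 0.8 SD of change.** Noncentrality is 0.8/√(2/25) = 2.828 on 48 df. Power is 82% uncorrected and 79% with the unbiased variance and t reference. It is 78% with Mancl-DeRouen.

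**The case against.** **The plan does not say that the intervals are uncorrected.** This stands. A reader might infer that 4.2 specifies a faulty interval, but the text is silent, and the statistician may already intend a correction. Section 4.2 names no test either. An uncorrected robust score test would be equally consistent with it and holds 5.1% (1 df) and 5.0% (2 df) at 25 per arm without covariates. The figures above therefore concern Wald intervals and Wald p-values only.

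**Many survey items are not continuous.** This also stands, and it limits the point. Appendix C contains many yes/no items, and scoring is not described. A simulated yes/no outcome measured twice (logit link, uncorrected robust Wald, 25 per arm, assumed correlation 0.3 to 0.7) gave a level of 5.4–5.8% at prevalence 0.5 to 0.7, 4.6–4.9% at 0.8 and 1.4–2.4% at 0.9. At 0.9 about a quarter of replicates could not be estimated. It is tempting to say that all the trial's intervals are too narrow, but that does not follow.

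**The primary outcomes cannot be assigned to one case.** Two surveys give a single change contrast, and three time points allow a 2-df test. A single contrast has 93.9% coverage either way, but the 7.0% figure applies to primary outcomes only if three surveys are taken.

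**The effect is small for a non-randomised pilot.** This is true, and it is why the point ranks low. It does not argue against a one-sentence clarification.

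**Conclusion.** The point holds as a minor one, an optional improvement. If the robust intervals are uncorrected Wald intervals, then for continuous, approximately normal outcomes at 25 per arm a single contrast runs at 6.1% instead of 5%, and a three-time-point joint test runs at 7.0%. If section 3.6 reduces the analysed number to an assumed 20 or 15 per arm, the single-contrast level becomes 6.4% or 6.9%. An assumed three to five covariates raise it to about 7–8% at 25 per arm, but only if they enter the tested contrast. A reader might infer that the P<0.10 screen inflates the error by itself, and the documents do not support this because they do not say how the covariates enter the model.

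Confidence is high in the arithmetic under its stated assumptions. It is lower on whether the uncorrected form will actually be used. Self-selection into arms, acknowledged in sections 2.6 and 3.1, limits causal claims far more, and correcting the variance does not touch it.

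**What to change.** Add to section 4.2: for continuous outcomes, GEE confidence intervals and Wald tests will use a bias-corrected sandwich variance (for example Kauermann-Carroll) with a t or F reference on between-participant degrees of freedom. Confirm that SAS version 9.2, named in 4.2, can produce it. State the number of survey time points consistently in 3.4 and 4.2, so that the primary contrast and its degrees of freedom are known. The correction was checked here for normal outcomes only. Yes/no items need a separate statement of method.

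**Cost.** One or two sentences, with no change to recruitment or visits. Without covariates, intervals are about 5% wider (1/0.955 = 1.047), and power at the assumed 0.8 SD falls from 82% to 79%. With five covariates in the contrast, intervals are about 11% wider. Mancl-DeRouen is a more conservative alternative, with intervals 7% wider without covariates and 20% wider with five. Kauermann-Carroll becomes very slightly liberal (5.3%) at an assumed 20 per arm with five covariates.

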1.2. Hypothesis

Research Question: Among guardians of children ages 6-12 years who are obese or overweight, does a family-based, culturally-tailored, virtual intervention change knowledge, self-efficacy, and behaviors about modifiable lifestyle practices to promote healthy eating when compared to standard in-office counseling?

Ho: A family-based, culturally-tailored, virtual intervention does not significantly change knowledge, self-efficacy, and behaviors about modifiable lifestyle practices when compared to standard in-office counseling.

Ha: A family-based, culturally-tailored, virtual intervention does significantly change knowledge, self-efficacy, and behaviors about modifiable lifestyle practices when compared to standard in-office counseling.

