2.3. Duration of Study

Participants will be part of the study for 6 months. This includes study recruitment, consenting, initial and subsequent in-office counseling, and x-IHPC for families enrolled in the intervention.

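### Four co-equal primary domains are each tested at p<0.05 against one joint null hypothesis, with no rule for what rejects it and no settled survey time point

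*Combined protocol and SAP*

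**What the plan says.** **Hypotheses.** Section 1.2 gives one null and one alternative. The alternative is that the intervention "does significantly change knowledge, self-efficacy, and behaviors about modifiable lifestyle practices" compared with in-office counselling. Knowledge, self-efficacy and behaviours stand together in a single statement.

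**Primary analysis.** Section 4.2: "Primary analyses will examine diet quality, screen time, physical activity, and guardian self-efficacy and confidence of those in the intervention and control groups". The method is GEE with robust confidence intervals, and the criterion is "A 2-sided p-value <0.05 will be accepted to indicate statistical significance". The abstract (Statistical Methodology) describes the same analysis as being "to assess if mean differences exist on dietary measures, screen time, physical activity and guardian self-efficacy and confidence". Neither place ranks the domains or says which contrast (a group effect, or group by time at a given visit) decides.

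**Time points.** Section 4.2 lists "baseline, post-intervention, and 6-month post-intervention". Section 3.4 collects the survey "at the outset of the study and then again at the conclusion of the study". Section 2.3 says "Participants will be part of the study for 6 months". The abstract (Study Methodology) places counselling at visit 1, 3 months and 6 months, with a 12-week programme for the intervention group.

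**Instrument.** Section 3.4 allows survey items to change after community feedback, then closes the matter: "The final survey instrument will be submitted to this IRB for approval before the data collection begins". That fixes the questions. It does not say how the items form a domain score.

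**The concern.** With one joint null, four primary domains and no success rule, the same results can be reported in opposite ways. If one domain gives p<0.05 and three do not, the null is rejected under an any-one rule and not rejected under an all-domains rule. The plan states neither, so the choice could be made after the results are seen. Under the first rule the chance of a false claim rises above 5%. Under the second it does not, but power falls.

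Two further gaps widen the room for choice. The deciding time point is not named, and the sections disagree on how many survey points exist. Knowledge is part of what the null asserts, but it is not among the outcomes listed in the abstract, Section 3.4 or Section 4.2, so no listed analysis bears on that part of the null.

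**Working it through.** **Inputs from the plan.** Per-test level 0.05, two-sided (Section 4.2). Four primary domains (Section 4.2). 25 per group (Section 4.1), and 25 + 25 = 50 agrees with the stated total. The plan gives no power, effect size, SD or family-wise error rate, so there is no stated operating figure to reproduce.

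**Assumptions, none of them in the plan.** Test statistics are normal with a common correlation r between domains. The groups are comparable, so that each test holds its nominal 5%. The success rule is as named in each step.

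**1. Any one domain suffices, one test per domain.**
- At r = 0: 1 − 0.95⁴ = 1 − 0.8145 = 18.5%.
- At r > 0: 1 − ∫ φ(x) [Φ((c − √r·x)/√(1−r)) − Φ((−c − √r·x)/√(1−r))]⁴ dx, with c = 1.96.

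| Tests | r = 0 | r = 0.5 | r = 0.8 | r = 0.9 |
|---|---|---|---|---|
| 4 (one per domain) | 18.5% | 15.6% | 11.4% | 9.4% |
| 5 (self-efficacy and confidence scored separately) | 22.6% | 18.3% | 12.7% | 10.2% |
| 8 (four domains at two post-baseline points) | 33.7% | 25.0% | 15.7% | 11.9% |

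The eight-test row uses the same formula with exponent 8 (at r = 0, 1 − 0.95⁸ = 33.7%). It needs the three survey points of Section 4.2. With the two points of Section 3.4 there is only one post-baseline survey, so one score per domain gives four tests.

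**2. All four domains must succeed.** The false-positive rate is at most 5%. The cost is power: the chance that all four succeed is 0.8⁴ = 41.0% at r = 0, rising to 70.2% at r = 0.9, if each domain has 80% power. It is 0.5⁴ = 6.2% rising to 36.9% if each has 50%.

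**3. Holm across the four.** The first step uses 0.05/4 = 0.0125. With no true effects, family-wise error is 1 − 0.9875⁴ = 4.9% at r = 0 and 2.6% at r = 0.9.

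**4. Detectable effect at 80% power, 25 per arm, no attrition.** Two-sample t-test, noncentral t, 48 df: 0.81 SD at 0.05 and 0.98 SD at 0.0125. Adjusting for baseline multiplies the standard error by √(1 − ρ²). At an assumed baseline-to-follow-up correlation ρ = 0.5 (47 df) the figures are 0.70 and 0.85 SD.

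**5. Time points side by side.** A survey taken only at outset and conclusion cannot feed the three-point primary analysis of Section 4.2. The third point has two readings. As the 6-month clinic visit in the abstract, it fits the participation period of Section 2.3. As six months after a 12-week programme that starts near visit 1, it falls at about 3 + 6 = 9 months, beyond that period.

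**The case against.** The strongest reply is that this is a pilot of 50 families with no power claim. The abstract speaks of mean differences on each measure, Section 4.2 already plans robust confidence intervals, and reporting every domain separately is a natural reading. That has weight and shapes the preferred fix. It does not settle the matter, because Section 1.2 states a formal null and alternative, Section 4.2 sets a significance threshold, and Section 4.1 speaks of testing effectiveness.

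It may also be said that the any-one rule is assumed. It is. A reader might infer that the plan adopts it, but the plan adopts no rule, and that is the gap.

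A reader might also take 18.5% or 33.7% as this trial's error rate. The documents do not support that. Section 2.6 lets families choose their arm and concedes selection bias, and Section 3.3 has no randomisation, so the tests need not hold 5% even singly.

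A third inference would be that the last survey necessarily falls after participation ends. The 3- and 6-month visits allow a consistent reading, so that conflict is only conditional. The conflict between two and three survey points stands.

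Finally, scoring rules may exist in the published instruments that the survey adapts, which cannot be checked here. The plan itself states none. Nor does the allowance for changing items mean that they can be altered once data arrive, since Section 3.4 requires the final instrument to be submitted for approval first.

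**Conclusion.** The point holds in conditional form. Four co-equal primary domains are each judged at an unadjusted two-sided 0.05 against one joint null, with no decisive domain or time point, success rule or multiplicity control. If any one domain may reject the null, family-wise error is 9.4% to 18.5% with one test per domain, and 11.9% to 33.7% with two post-baseline tests per domain, over correlations 0.9 to 0 and assuming comparable groups. The two-versus-three survey points and the unmeasured knowledge component are plain inconsistencies that need no assumption. The matter affects what the trial may conclude and should be settled in writing before analysis. It ranks as a clarification the sponsor should make, and it is separate from the self-selection bias.

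**What to change.** Before analysis:

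1. Reconcile the abstract and Sections 2.3, 3.4 and 4.2 on the number and dates of survey points. Keeping the two points of Section 3.4 needs no extra data collection. Three would add a round of phone surveys.
2. Write down one score per domain. Either link knowledge to listed survey items or remove it from the null and alternative.
3. In keeping with the pilot label, treat the four domains as exploratory: report all estimates and confidence intervals, and make no reject or not-reject statement about the joint null.
4. If a formal test is kept, rewrite the null to match it. Either name one domain score at one time point, tested at 0.05, or state separate domain hypotheses tested with Holm at one time point and claim effects only for domains that pass.

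**Cost.** No extra enrolment. The exploratory route gives up a confirmatory claim. A single named primary keeps the detectable effect at 0.81 SD. Holm raises it at the first step to 0.98 SD (or from 0.70 to 0.85 SD with baseline adjustment at ρ = 0.5). These effects come from a t-test rather than robust GEE and ignore attrition, although Section 3.6 drops the data of families who leave. The baseline-adjusted figures also presume balanced baselines, which self-selection makes doubtful. None of these steps removes the self-selection bias.

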4.3. Data Storage

4.3.1. Data Management

Information about study subjects will be kept confidential and managed according to the requirements of the Health Insurance Portability and Accountability Act of 1996 (HIPAA). Privacy and confidentiality of all enrolled participants will be maintained.

The PI and co-PI at HWNV will have an electronic list of participants who are part of the study so they can provide the standard in-office counseling and data collection. The list will be accessed only by them on a password-protected document that is stored on password-protected computers at HWNV.

Survey data collected during the study will be uploaded directly into a secure online platform, RedCap, by the CHW collecting the data. Only the study PIs will have access to this platform to manage data.

